## **8. RESEARCH QUESTION AND OBJECTIVES**

The overall objective of the present IPF Registry is to gain further insight on the characteristics, management, disease progression and the outcomes of patients with IPF, as diagnosed and treated under real-world, clinical practice conditions in Greece.

More specifically, this registry will be used to:

- Provide a comprehensive clinical picture of IPF
- Track access to health care and cost of caring for IPF patients over time
- Examine the implementation of treatment guidelines [2], used on patients diagnosed with IPF, according to the existing diagnosis guidelines [1]
- Characterization of patients on different treatments

Furthermore, this project aims to provide information regarding survival and mortality causes, IPF exacerbations as well as IPF patient co-morbidities including myocardial infarction, CNS infarction, other arterial thromboembolic events, deep vein thrombosis, hemorrhage, gastrointestinal perforation and pulmonary hypertension (please refer to [Annex 3](#)). In addition, data regarding IPF patient hospitalization will be collected and evaluated with regards to potential respiratory causes, and there will be documentation of treatment patterns and economic aspects. Patients will be followed up for 2 years and information regarding IPF treatment changes since the last visit will be collected.

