### Collection of AEs

The study design is of non-interventional nature and the study is conducted within the conditions of the approved marketing authorisation. Sufficient data from controlled interventional trials are available to support the evidence on the safety and efficacy of Nintedanib. For this reason the following AE collection and reporting requirements have been defined.

The following must be collected by the investigator in the (e)CRF from signing the informed consent onwards until the end of the study:

- all ADRs related to Nintedanib, taken for idiopathic pulmonary fibrosis (serious and non-serious),
- all AEs with fatal outcome in patients exposed to Nintedanib, taken for idiopathic pulmonary fibrosis

All ADRs, including those persisting after study completion must be followed up until they are resolved, have been sufficiently characterized, or no further information can be obtained.

The investigator carefully assesses whether an AE constitutes an ADR using the information below.

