#### Intensity of adverse event

The intensity of the AE should be judged based on the following:

Mild: Awareness of sign(s) or symptom(s) which is/are easily tolerated

Moderate: Enough discomfort to cause interference with usual activity

Severe: Incapacitating or causing inability to work or to perform usual activities

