Hemorrhage	
a) Location:
 

a. Gastrointestinal hemorrhage

b. Intracranial hemorrhage

c. Rectal hemorrhage

d. Epistaxis

e. Hemorrhage NOS

 
b) Severity:
 

a. Major bleeding, defined as meeting one or more of the following criteria):

i. Overt bleeding associated with a reduction in hemoglobin of at least 20 grams per liter or leading to a transfusion of at least 2 units of blood or packed cells

ii. Symptomatic bleeding in a critical area or organ: Intraocular, intracranial, intraspinal or intramuscular with compartment syndrome, retroperitoneal bleeding, intra-articular bleeding or pericardial bleeding

iii. Life-threatening bleeding

iv. Fatal bleeding

b. Life-threatening bleeding, as defined as meeting one or more of the following criteria:

i. Symptomatic intracranial bleed

ii. Reduction in hemoglobin of at least 50 grams per liter

iii. Transfusion of at least 4 units of blood or packed cells, associated with hypotension requiring the use of intravenous inotropic agents

iv. Necessitated surgical intervention

v. Fatal bleeding

 
c) Circumstances:
 

c. peri/postoperative

d. accident/ injury

e. other (please specify)

f. unknown

Gastrointestinal perforation	

a) Perforation of gastric ulcer

b) Perforation of duodenal ulcer

c) Perforation of small-intestine diverticulum

d) Perforation of colon diverticulum

e) Peritonitis as a complication of appendicitis

f) Perforation as procedural complication (endoscopy),

Proprietary confidential information © 2018 Boehringer Ingelheim International GmbH or one or more of its affiliated companies

OUTCOME	DEFINITION
	g) Others (please specify)
Pulmonary hypertension	a) Right-heart catheterization performed (mPAP>25 mmHg at rest) b) No RHC performed / Diagnosed by echocardiography or clinical diagnosis

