## **6.6 HANDLING OF MISSING DATA AND OUTLIERS**

No imputation technique to fill in any missing values will be performed. Accordingly the Last Observation Carried Forward technique will not be applied.

Missing values will be differentiated from negative answers.

Summary statistics will be performed only on subjects with available information (unknown data will not account in the total population for each specific variable).

For missing or incomplete AE dates or drug administration dates, or other significant dates, the BI internal procedures and guidelines will be employed.

Missing dates related to AE events will not be imputed since no analysis based on duration of AEs or time to event will be employed:

Missing dates related to deaths will be handled according to BI standards and therefore, no subjects with incomplete date of death will be included in the time to event analysis.

Regarding outliers, the distributional properties should be examined by PP and/or QQ plots in conjunction with the summary statistics of mean/median/SD. Should the distributional properties of a variable indicate the existence of outliers, then the values will not be neglected from the analysis, but the variance will be reduced following the logarithmic transformation. Any implausible data will be treated separately and it will be judged based on case by case basis.

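### The haemorrhage severity item in Annex 3 has no code for a bleed that meets none of its criteria, so an assessed non-major bleed cannot be told apart from an unassessed one

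*Protocol*

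**What the plan says.** - **What is collected.** Protocol section 8 lists the conditions on which the registry will report, including "other arterial thromboembolic events, deep vein thrombosis, hemorrhage, gastrointestinal perforation and pulmonary hypertension". It does not restrict haemorrhage to major bleeds. Table 1 has the Annex 3 outcomes recorded at baseline (for the past 12 months) and at follow-up.
- **Location.** The Annex 3 haemorrhage row lists gastrointestinal, intracranial and rectal bleeding, epistaxis, and "Hemorrhage NOS". No location carries a severity threshold.
- **Severity.** There are two entries: "Major bleeding, defined as meeting one or more of the following criteria" and "Life-threatening bleeding, as defined as meeting one or more of the following criteria". The lowest numeric bar for major is "Overt bleeding associated with a reduction in hemoglobin of at least 20 grams per liter or leading to a transfusion of at least 2 units". Life-threatening bleeding is the third criterion for major, and fatal bleeding is listed under both entries.
- **Circumstances.** This item, in the same row, includes both an other and an unknown option. Severity has neither.
- **Analysis.** SAP 6.6 rules out imputation, promises to separate missing values from negative answers, and states that "unknown data will not account in the total population for each specific variable". SAP 7 says that percentages in categorical tables are relative, unless otherwise specified, to all subjects in the set, with or without a value. Protocol 9.8.1 describes follow-up events by incidence rates with 95% confidence intervals.

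**The concern.** The location list lets in minor bleeds, but the severity item cannot describe them. A site that assesses a bleed and finds that no criterion is met has nothing to enter. Once the data are collected, the analyst cannot tell that bleed from one whose severity nobody assessed, and no analysis can recover the difference.

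What is at stake is the severity breakdown of one named descriptive outcome. As Annex 3 is written, the proportion of bleeds that were non-major cannot be stated, and a percentage among classified bleeds carries no information.

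**Working it through.** The plan states no figure on this point, so there is none to reproduce. The check is a logical one on the Annex 3 definitions, followed by the effect of each SAP denominator.

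**1. Criteria.** The severity item uses seven distinct criteria:
- listed directly under major only: haemoglobin fall of at least 20 g/L or transfusion of at least 2 units; bleeding in a critical area or organ;
- listed under life-threatening: symptomatic intracranial bleed; haemoglobin fall of at least 50 g/L; at least 4 units with hypotension needing inotropes; surgical intervention; fatal bleed (also listed under major).

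Life-threatening bleeding is itself a criterion for major. So life-threatening = any of the last five, and major = any of the seven.

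**2. Enumeration.** Each criterion is met or not met, giving 2^7 = 128 patterns.

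| Result as written | Count | Arithmetic |
|---|---|---|
| Major and life-threatening | 124 | (2^5 − 1) × 2^2 = 31 × 4 |
| Major only | 3 | 2^2 − 1 |
| Life-threatening but not major | 0 | subset |
| No code | 1 | no criterion met |
| Total | 128 | 124 + 3 + 1 |

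All 127 patterns that receive a severity are major. These are logical patterns, not frequencies, and some will not occur in practice. The one pattern without a code is a bleed that meets no criterion.

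**3. What a blank means.**

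| True state | Available entry |
|---|---|
| Assessed, at least one criterion met | major, with life-threatening where it applies |
| Assessed, no criterion met | none, so blank |
| Not assessed or unknown | none, so blank |

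The last two states share one value. The separation that SAP 6.6 promises therefore cannot be made for this field.

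**4. Effect of the denominator.** Let H be the recorded bleeds and u the share that meets no criterion and is left blank. The documents give no value for u, so the range below is assumed.
- Share major among all recorded bleeds = H(1 − u)/H = 1 − u.
- Share major among classified bleeds (SAP 6.6) = H(1 − u)/H(1 − u) = 100% for any u below 1.

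| u (assumed) | Share major, all recorded bleeds | Share major, classified bleeds only |
|---|---|---|
| 25% | 75% | 100% |
| 50% | 50% | 100% |
| 75% | 25% | 100% |
| 90% | 10% | 100% |

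Under the SAP 7 default the denominator is all subjects. If, say, 4 of about 300 patients had a major bleed (assumed count), the table would show 4/300 = 1.3%. That figure is not 100%, but it too says nothing about how many bleeds were assessed and found non-major. The two SAP rules give different answers, and neither is tied to this variable.

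**The case against.** **Annex 3 defines outcomes and is not the form.** It does not call severity a mandatory single choice. If the two entries are separate flags, a bleed with neither flag could be read as non-major. This stands in part: the eCRF is not in the documents and may offer such flags or another option. But no section says that an empty severity means non-major, and Annex 3 gives no unknown option either.

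**The adverse event scale may cover minor bleeds.** Protocol 11.2 grades adverse events as mild, moderate or severe. However, collection is limited to reactions related to nintedanib and to fatal events in patients exposed to it. Other minor bleeds get no grade, so the cover is partial.

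**Nesting is ordinary.** Life-threatening within major is a normal hierarchy and not an error. This stands. It only needs a statement that the levels are not exclusive.

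A reader might also infer more than the documents support:
- *That the report will show 100% major whatever the data.* This follows only if the bleeds are left blank and the SAP 6.6 denominator is used. SAP 7 gives another default. The SAP endpoint list names no haemorrhage severity item, and the display plan it cites is not among the documents.
- *That major bleeds will be over-counted.* This needs sites to tick major for bleeds that fail its written criteria, and nothing in the documents suggests that they will.
- *That no nosebleed can be classified.* One with a sufficient haemoglobin fall, transfusion or surgery can be.
- *That the bleeding-risk item adds weight.* Annex 4 defines it by predisposition, ulcers, injury or surgery, and anticoagulant use. It is a different variable from bleeding events.

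**Conclusion.** The point holds as a gap in data capture. On the text of Annex 3, a bleed that meets none of the criteria has no severity code, and non-major cannot be separated from not assessed, contrary to the intent stated in SAP 6.6. The conclusion that every classified bleed is major rests on two conditions: blanks for non-major bleeds, and a denominator of available data only. SAP 6.6 and SAP 7 need to be reconciled for this variable.

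The reach is limited to the severity breakdown of one descriptive outcome. Total haemorrhage incidence can be counted from the location entries, and the count and rate of major bleeds stay valid if sites apply the written criteria. The size of the information loss depends on the share of minor bleeds, which the documents do not give. The change is worth making because the loss cannot be repaired after collection. If the eCRF already holds a suitable option, only Annex 3 and the SAP need to be aligned with it.

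**What to change.** 1. In Annex 3 and the eCRF, add two severity options: non-major (meets none of the listed criteria) and unknown.
2. State that life-threatening is a subset of major, and report major, of which life-threatening.
3. In the SAP, set the denominator for haemorrhage severity as all recorded haemorrhages, with unknown shown on its own line, and say that this overrides the general rules in SAP 6.6 and SAP 7 for this variable.

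The cost is one Annex 3 edit, a small eCRF change, one SAP sentence, and a one-off query to sites for bleeds already entered. The change concerns how bleeds are recorded and does not touch patient management.

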## **ANNEX 4 ASSESSMENTS OF VARIABLES**

Variable	Categories
Type of site	

- Categorical:

• General practice/primary care

• Specialist office

• Community hospital

• University hospital

• Out-patient health care centre

• Anticoagulation clinics

• Other (please specify)

Age [years]	
Calculated as the difference between date of birth and date of informed consent, convert to years (divided by 365.25) and lower truncated to the integer.
 
Continuous and categorized as:
 

- 40-44

- 45-54

- 55-64

- 65-74

- <math>\geq 75</math>

- Unknown

 
Additionally categorized as <math>\leq 65</math>, <math>> 65</math>
 
<Please specify the category of reference if comparisons are foreseen e.g.:
 

• - <math>\leq 65</math> years vs. <math>> 65</math> years old,

Race	
Categorized as:
 

- American Indian or Alaska Native

- Asian

- Black or African American

- Native Hawaiian or other Pacific Islander

- White

- Other

 
Not reported

Gender	
Categorized as:
 

• Male

 
Female

Smoking status	

- Categorized as:

Never / Past / Current / Unknown

 
For the Past/Current, specify packs/year and for Past (number of years smoking one pack per day equivalent)

Drugs of abuse	

- Categorized:

• Alcohol consumption: Drinker/ex-drinker/non-drinker/unknown

Proprietary confidential information © 2018 Boehringer Ingelheim International GmbH or one or more of its affiliated companies

Variable	Categories
	
 
• Cocaine consumption: Never / Past / Current / Unknown
 
Other,(please specify)
 

Family history of pulmonary fibrosis	
 
- Categorized as: Yes/No/Unknown
 

Environmental and occupational exposures	
 
- Any exposure ticked in this category (Yes/No/Unknown): 
 
• Metal dusts (brass, lead, and steel)
 
• Wood dust (pine)
 
• Farming
 
• Raising birds
 
• Hair dressing
 
• Stone cutting/polishing
 
• Asbestos
 
• Solvents
 
 
 

Exposure to drugs associated with IPF	
 
- Any exposure ticked in this category (Yes/No/Unknown): 
 
• Amiodarone
 
• Bleomycine
 
• Nitrofurantoin
 
• Methotrexate
 
 
 
- Gold salts
 

Exposure to viral infection with potential association with IPF	
 
- Serum antibodies for (Positive/Negative/not available) 
 
• Ebstein-Barr Virus
 
• Hepatitis C virus
 
 
 
Other positive (please specify)
 

Diagnostic procedures that were used during diagnostic workout	
 
- Date: DD-MMM-YYYY
 
- High-Resolution Computed Tomography [HRCT] 
 
- UIP pattern
 
- Possible UIP pattern
 
- Inconsistent UIP pattern
 
- Not available
 
 
 
- Histology (lung biopsy) 
 
- UIP pattern
 
- Probable UIP pattern
 
- Possible UIP pattern
 
- Inconsistent with UIP or non-classifiable
 
 
 
- Not available
 

Date when IPF was diagnosed	
 
- Format: DD-MMM-YYYY
 

Lab values	At enrolment, to exclude connective tissue disease (positive/negative/not performed/unknown/performer but missing value) and value (units):

Variable	Categories
	
 
• Rheumatoid factor
 
• Anti-cyclic citrullinated peptide (anti-CCP)
 
• Anti-nuclear antibodies (ANAs)
 
• Scl-70
 
• SS-A
 
• SS-B
 
• Other biomarker of autoimmune disease (please specify)
 

Vital signs and physical examination	
 
- Continuous and categorical, as appropriate.
 
- Categorized as Yes/No/Unknown and further categorized as (examples) : 
 
• Heart rate (BPM)
 
• Blood pressure (mmHg)
 
• Weight
 
• Height
 
• Date: DD-MMM-YYYY
 
 
 

Pulmonary function testing	
 
- Continuous 
 
• FVC (mL, % pred)
 
• VC (mL, % pred)
 
• TLC (mL, % pred)
 
• DLCO (mmol/min/kPa, % predicted Hb corrected)
 
• FEV1 (mL, % pred)
 
 
 
- Further categorized as: Yes/No/Unknown Date of pulmonary function testing: DD-MMM-YYYY
 

Biomarkers of autoimmune disease	
 
- Lab values of interest include (continuous): 
 
• Hb (g/dL),
 
• AST (µg/L)
 
• ALT (µg/L)
 
• Total bilirubin (mg/dL)
 
• BNP (ng/L)
 
• NT pro-BNP (ng/L)
 
 
 
- Further categorized as: Yes/No/Unknown • Date: DD-MMM-YYYY
 

Bleeding risk	
 
- Genetic predisposition (please specify)
 
- Gastrointestinal ulcers
 
- Major injury or surgery
 
• Use of anticoagulants
 

Thrombotic risk	
 
• Genetic predisposition (please specify)
 

Concomitant medications, please assess for each start/stop date and dose	
Any co-medication ticked in this category (Yes/No/Unknown)
 
 
• Corticosteroids
 
• NAC
 
• Azathioprine
 
• Cyclophosphamide
 

Variable	Categories
	

• Cyclosporine A

• Other immuno-suppressant (e.g. mycophenolate mofetil)

• Pirfenidone

• Anticoagulant

• Vit-K antagonist

• Heparin

• NOAC

• Other

• High-dose antiplatelet therapy

• GERD medication

• PDE-5 inhibitor

• Endothelin receptor antagonist

• Long-term Oxygen therapy

• Listed for lung transplantation

• NSAIDs

• Hormonal contraceptives

• Hormone replacement therapy

• Anti-VEGF drugs

Current participation in pulmonary rehabilitation program	

- Categorized as: Yes/No/ Unknown

Listing for or participation in lung transplantation	

- Categorized as: Yes/No/Unknown

- Date since when: DD-MMM-YYYY

Vital status	

Categorized as: Yes/No/Unknown

.

Pulmonary function testing	

- Continuous

• FVC (mL, % pred)

• VC (mL, % pred)

• TLC (mL, % pred)

• DLCO (mmol/min/kPa, % predicted Hb corrected)

• FEV1 (mL, % pred)

- Further categorized as: Yes/No/Unknown

• Date of pulmonary function testing: DD-MMM-YYYY

Hospitalizations	

- Categorized as: Yes/No/Unknown If yes: further categorized as:

• with/without ER use

• with/without ICU use

• with/without mechanical ventilation

• with/without ambulance use

- Date of hospitalizations:

• Known/Unknown

• If known: DD-MMM-YYYY

Proprietary confidential information © 2018 Boehringer Ingelheim International GmbH or one or more of its affiliated companies

Variable	Categories
	

- Discharge or death date:

• Known/Unknown

• If known: DD-MMM-YYYY

## **ANNEX 5. COMMON COMORBIDITIES OF INTEREST (RECODER WITH START, AND IF APPLICABLE STOP DATE)**

- Previous Haemorrhages
- Cardio and cerebrovascular comorbidities: Arterial hypertension, coronary artery disease (CAD), myocardial infarction (MI), congestive heart failure (CHF), CNS Infarction, transient ischaemic attack (TIA), peripheral artery disease, atrial fibrillation, deep venous thrombosis, pulmonary embolism, pulmonary hypertension
- Respiratory comorbidities: chronic obstructive pulmonary disease (COPD), emphysema (radiologic), asthma, pneumonia, obstructive sleep apnea
- Renal comorbidities: chronic renal failure (see definition in Section 14.2)
- Hepatic comorbidities: chronic hepatic failure, cirrhosis
- Gastrointestinal comorbidities: gastroesophageal reflux disease (GERD), gastric ulcer, appendicitis, abdominal surgery, inflammatory bowel disease (e.g. Crohn's disease, ulcerative colitis), GI cancer, diverticulitis, superior mesenteric artery syndrome
- Metabolic comorbidities: T2/T1 diabetes mellitus, hyperlipidaemia, hypothyroidism
- Neoplasms: lung, liver, stomach, colorectal, breast and oesophageal, prostate and cervix cancer
- Depressive disorder, anxiety disorder.

**ANNEX 6. HIGH RESOLUTION COMPUTED TOMOGRAPHY  
CRITERIA FOR USUAL INTERSTITIAL PNEUMONIA  
PATTERN (UIP) [1]**

UIP Pattern (All Four Features)	Possible UIP Pattern (All Three Features)	Inconsistent with UIP Pattern (any of the Seven Features)
Subpleural, basal predominance  Reticular abnormality  Honeycombing with or without traction bronchiectasis  Absence of features listed as inconsistent with UP (see column 'Inconsistent with UIP Pattern', on the right)	Subpleural, basal predominance  Reticular abnormality  Absence of features listed as inconsistent with UP (see column 'Inconsistent with UIP Pattern', on the right)	Upper or mid-lung predominance  Peribronchovascular predominance  Extensive ground glass abnormality (extent>reticular abnormality)  Profuse micronodules (bilateral, predominantly upper lobes)  Discrete cysts (multiple, bilateral, away from areas of honeycombing)  Diffuse mosaic attenuation/air-trapping (bilateral in three or more lobes)  Consolidation in bronchopulmonary segment(s)/lobe(s)

## **ANNEX 7. HISTOLOGICAL CRITERIA FOR UIP PATTERN IN LUNG BIOPSY [1]**

UIP pattern (all 4 criteria)	Probable UIP pattern	Possible UIP pattern (all 3 criteria)	Not UIP pattern (any of the 6 criteria)
Evidence of marked fibrosis/ architectural distortion,±honeycombing in a predominantly subpleural/paraseptal distribution	Evidence of marked fibrosis/ architectural distortion,±honeycombing	Patchy or diffuse involvement of lung parenchyma by fibrosis, with or without interstitial inflammation	Hyaline membranes*
Presence of patchy involvement of lung parenchyma by fibrosis	Absence of either patchy involvement or fibroblastic foci, but not both	Absence of other criteria for UIP (see 'UIP Pattern column')	Organizing pneumonia*†
Presence of fibroblast foci	Absence of features against a diagnosis of UIP suggesting an alternate diagnosis (see fourth column 'Not UIP pattern')	Absence of features against a diagnosis of UIP suggesting an alternate diagnosis (see fourth column) 'Not UIP pattern')	Granulomas†
Absence of features against a diagnosis of UIP suggesting an alternate diagnosis (see fourth column 'Not UIP pattern')	Or  Honeycomb changes only‡		Marked interstitial inflammatory cell infiltrate away from honeycombing
			Predominant airway centered changes
			Other features suggestive of an alternate diagnosis

\*Can be associated with acute exacerbation of idiopathic pulmonary fibrosis.

† An isolated or occasional granuloma and/or a mild component of organizing pneumonia pattern may rarely be coexisting in lung biopsies with an otherwise UIP pattern .

‡This scenario usually represents end-stage fibrotic lung disease where honeycombed segments have been sampled but where a UIP pattern might be present in other areas. Such areas are usually represented by overt honeycombing on HRCT and can be avoided. By using HRCT the pre-operative targeting of biopsy sites is performed away from these areas.

